1.1 Analysis Population

There is a required update to the SAP which will differ from the CSP. It related to the analysis populations in section 2.2 of the SAP. The analysis populations are taken directly form the CSP but has led to a misinterpretation which in turn has led to data being missed from the analysis which could be utilized.

The update relates to the Evaluable analysis set but impacts the Primary analysis set as well. The updated definition is outlined in Table 1.

Population/Analysis Set	Description
Evaluable	All participants who have completed three doses of study
	intervention and have baseline and post-benralizumab treatment
	study evaluation in at least one of PROs, CT scans, or spirometry
	tests – the evaluable population.

Table 1 Analysis Data Sets

The update resolves the issue that a missing PRO, for example, would lead to available spirometry tests or CT scan data not being presented. It has been clarified that only one of these need to be present to be included in the analysis set.

1.2 Visit 4 Window

In sections 2.4.2 of the SAP, visit 4 is defined as Week 13 ± 5 days. There are many participants whose visit 4 date falls outside their window defined in the protocol and the SAP. This means many participants removed from the analysis. It has been decided that the window for visit 4 should be removed entirely as all visit 4 visits should be included in the analysis.

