center) will be discontinued from the study (see Section 7.1) and procedures for an Early Study Intervention Discontinuation (E/D) follow-up should be followed as described in the SoA. (Refer to Table 1 for data to be collected at the time of discontinuation of study intervention and follow-up and for any further evaluations that need to be completed).

Participants who have an asthma exacerbation (worsening of asthma) or respiratory tract infection that does not require hospitalization (defined above), but require use of antibiotics and/or systemic corticosteroids (or a temporary increase in a stable oral corticosteroid background dose) for at least 3 days [a single depo-injectable dose of corticosteroids will be considered equivalent to a 3-day course of systemic corticosteroids] should have their visit schedule adjusted per the following guidance, according to when it occurs:

- Before Visit 1 (V1), this visit should be rescheduled to occur after resolution of the exacerbation/infection and at least 4 weeks after the last dose of any medication to treat the exacerbation/infection, provided that there are no safety concerns as judged by the Investigator.
- Between Visit 1 (V1) and Visit 3 (V3), there will be no changes to the study activities and the SoA should be followed (Table 1).
- Between Visit 3 (V3) and Visit 4 (V4), the participant will be permitted to undergo the study assessments for Visit 4, but it should be delayed to ensure an interval between Visit 4 and the last dose of antibiotic or OCS, whichever ends later (or return of OCS dose to previous maintenance dose) of at least 7 days, but no longer than 14 days, per investigator's discretion.

In case of uncertainty related to procedures following an exacerbation, please consult with the AstraZeneca US study team.

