2.3.3 Handling of Unscheduled Visits

Any study assessment which is performed outside the visit window for a scheduled visit will be linked to an unscheduled visit. Data collected during unscheduled post-baseline visits will only be reported in the participant listings and will not be considered for summary tables. When unscheduled data are the last obtained before the first study intervention administration, they will be considered as baseline measurements, and will be included in summary tables.

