3.1.10 Sample Size Analysis

3.2 Endpoint Analyses

This section covers details related to the primary, secondary, tertiary, and safety endpoints, including sensitivity and supportive analyses. A summary of the planned endpoint analyses is provided in Table 3.

Details

category	Endpoint	Population	strategy	summary (analysis)	in Section
Primary objec benralizumab	ctive – To describe the c , using measurements f	hange from baselin rom untrimmed air	e in mucus volume at rways at TLC and irre	week 13 following treat spective of patient chara	ment with acteristics
Primary	Change from baseline (Week 0) at week 13 (± 5 days) in untrimmed total mucus volume at TLC	Evaluable set; Primary analysis population	Included in analysis regardless of treatment discontinuation, any IPD or any prohibited medication (treatment policy); Participants with exacerbations are excluded from the primary analysis set	Unadjusted mean within participant difference in untrimmed total mucus volume calculated as the mean change from baseline (Week 0) at Week 13 (± 5 days).	3.2.1
Secondary obj treatment with	jective 1 – To describe t h benralizumab, as mea	he change from ba sured by secondar	seline in airway dynan y FRI endpoints, irresj	nics at Week 13 followin pective of patient charac	g cteristics.
Secondary	Change from baseline (Week 0) at week 13 in primary and secondary FRI parameters ^a	Evaluable set; Primary analysis population	Included in analysis regardless of treatment discontinuation, any IPD or any prohibited medication (treatment policy); Participants with exacerbations are excluded from the primary analysis set	Unadjusted mean within participant difference, calculated as the mean change from baseline (Week 0) at Week 13 (± 5 days), in listed FRI endpoints.	3.2.2
Secondary obj measurements	jective 2 – To describe t s, cross-sectionally (at V	the relationship bet Veek 0) and irrespe	ween airway dynamics ective of patient charac	s and conventional lung cteristics.	function
Secondary	Baseline (Week 0) relationship between pre-BD FEV1 and: In primary and secondary FRI parameters ^a	Evaluable set; Primary analysis population; Baseline endpoints analysis set	Included in analysis regardless of treatment discontinuation, any IPD or any prohibited medication (treatment policy). Participants with exacerbations are excluded from the	 Spearman's rank correlation coefficient Pearson correlation Graphical summary (scatterplots) Regression coefficients with 95% CI 	3.2.3

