3.2.1.1 Definition

a

Table 4	Definition	of Primary	Endpoint
---------	------------	------------	----------

Population:	Evaluable set; Primary analysis population
Endpoint:	Change from baseline (Week 0) to week 13 in airway dynamics, using untrimmed total mucus volume at TLC
Treatment:	Benralizumab 30mg, 3 doses, once every 4 weeks (at baseline [V1], Week 4 [V2] and Week 8 [V3])
Intercurrent events:	Participant withdrawal, IPD, use of prohibited medicines/substances, asthma exacerbation (Participant with exacerbations will be excluded from the primary analysis set)

Population-level	Unadjusted within participant difference in total mucus volume (specific airway volume)
summary:	measured at TLC, calculated as the mean change from baseline (Week 0) at Week 13
	$(\pm 5 \text{ days})$

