2.6 Visit 4 Window

In sections 2.4.2 of the SAP, visit 4 is defined as Week 13 ± 5 days. There are subjects who have visit 4 outside of this window and given the small number of subjects it has been decided to be more flexible on which visits are allowed in the analysis. Although visits outside of the window will still be considered a protocol deviation we have the following classification:

- Up to five days outside of the window will be a non-important PD.
- Beyond five days outside of the window will be considered an important.

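### The Visit 4 analysis window is removed with no outer limit, but the primary endpoint is still labelled Week 13 (± 5 days) and nothing planned shows whether out-of-window visits change the estimate

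*SAP*

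**What the plan says.** The endpoint has a time window. SAP Table 3 (section 3.2) gives it as "Change from baseline (Week 0) at week 13 (± 5 days) in untrimmed total mucus volume at TLC". Table 4 (section 3.2.1.1) describes the summary as "measured at TLC, calculated as the mean change from baseline (Week 0) at Week 13", followed by the same ± 5 days. The protocol's objectives tables agree.

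The base SAP enforced the window. Section 2.3.3 says "Any study assessment which is performed outside the visit window for a scheduled visit will be linked to an unscheduled visit", and post-baseline data of that kind go to listings only.

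The addendum reverses this. Section 1.2 reports "There are many participants whose visit 4 date falls outside their window defined in the protocol and the SAP" and concludes that "the window for visit 4 should be removed entirely as all visit 4 visits should be included in the analysis". Section 2.6 keeps the window for one purpose, grading protocol deviations. A visit up to five days outside is non-important. For the rest, "Beyond five days outside of the window will be considered an important" deviation. SAP 3.1.3.2 reports important deviations as numbers and percentages.

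The addendum does not reword Tables 3 and 4 or SAP 2.3.3. SAP 3.2.1.6 and 3.2.1.7 (sensitivity and supplementary analyses of the primary endpoint) are both marked not applicable, and the addendum adds neither.

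**The concern.** Under the current rule the reported mean change will carry a Week 13 (± 5 days) label while including visits that the plan itself says lie outside those days. The label is then inaccurate, and a reader cannot tell how inaccurate.

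Timing matters to interpretation here. Protocol 4.2 chose the assessment time so that it would fall midway between the third and fourth doses, for reasons of serum concentration. Visits well away from the target do not share that rationale.

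The change concerns the primary endpoint of an open-label, single-arm trial and was made once visit dates were known. At stake is whether a reader can see that the conclusion does not depend on it.

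**Working it through.** **1. Put the timing rules on one scale.** Visit 1 is day 0, so week 13 is 13 × 7 = day 91 and the third dose (week 8) is day 56.

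| Source | Rule | Visit 4 study days |
|---|---|---|
| Protocol Table 1; SAP 2.3.2, Tables 3 and 4 | ± 5 days | 86–96 |
| Protocol 4.2 and 4.4 (duration, completion) | ± 1 week | 84–98 |
| Protocol synopsis | 4 to 6 weeks after Visit 3 | 84–98 if Visit 3 is on day 56; 79–103 if Visit 3 is anywhere in its own window (days 51–61) |
| Addendum 2.6, non-important deviation | up to 5 days outside | 81–85 and 97–101 |
| Addendum 2.6, important deviation | more than 5 days outside | before 81 or after 101 |
| Addendum 1.2, analysis | none | no limit |

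These rules do not agree with one another. A Visit 4 on day 98 meets the completion definition in Protocol 4.4 but lies outside ± 5 days. A Visit 3 on day 61 followed by Visit 4 on day 103 meets the synopsis rule (42 days) but is an important deviation under the addendum. A Visit 3 on day 61 followed by Visit 4 on day 86 meets both visit windows but leaves 25 days, under the synopsis minimum of 28.

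**2. Delays that the protocol permits.** Protocol 5.5.4 allows up to 14 days from a positive COVID-19 test. From the last in-window day this gives 96 + 14 = day 110 (week 15.7). Protocol 8.3.1 says that after an exacerbation or infection between Visits 3 and 4 "the participant will be permitted to undergo the study assessments for Visit 4, but it should be delayed", with 7 to 14 days after the last antibiotic or oral steroid dose. So some out-of-window visits are not conduct failures.

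**3. What the planned outputs would reveal.** Counts of important deviations cover only visits before day 81 or after day 101. Even these have no clear place among the four categories in SAP 2.3.5, where the only timing category is visits affected by COVID-19. No output gives the visit day or an estimate without these visits.

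**4. Size of a possible shift (illustration only).** The documents give no time course for mucus volume. Suppose a share f of visits is out of window and shows r times the week-13 effect. The estimate is then (1 − f + f·r) times the week-13 effect. With f from 10% to 50% and r from 0.5 to 1.5, the extremes are 1 − 0.5 + 0.5 × 0.5 = 0.75 and 1 − 0.5 + 0.5 × 1.5 = 1.25. The direction is open.

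**5. Precision of an in-window analysis.** The plan's figure of 29 cannot be reproduced, because the effect size, SD and power are not visible in Protocol 9.2. Solving a two-sided 5% paired t-test backwards at n = 29 gives a detectable standardised change of 0.539 at 80% power or 0.624 at 90%. With the SD unchanged, the half-width ratio is [t(0.975, n−1)/√n] ÷ [t(0.975, 28)/√29]. For n = 14 this is (2.160/3.742) ÷ (2.048/5.385) = 1.52.

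| Assumed share outside | n in window | Half-width ratio | Power if planned at 80% | Power if planned at 90% |
|---|---|---|---|---|
| 10% | 26 | 1.06 | 75% | 86% |
| 20% | 23 | 1.14 | 70% | 82% |
| 30% | 20 | 1.23 | 63% | 75% |
| 40% | 17 | 1.35 | 55% | 68% |
| 50% | 14 | 1.52 | 46% | 58% |

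**The case against.** The change is disclosed: the addendum lists it among its departures from the protocol. Discarding data in a trial of about 29 analysed participants would be costly, and the protocol itself permits some delay. The addendum opens only the analysis window; the protocol's conduct limits on Visit 4 remain. Deviation counts give some visibility. A restricted set could differ from the full set by chance alone, and ± 5 days is not the only documented window, so that restriction could drop visits the protocol counts as completed.

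Most of this stands, and it is why the all-visits analysis should remain the main one. It does not answer the narrower point. Disclosing the rule change leaves the endpoint label wrong, and counting deviations does not show whether they matter. The disagreement about windows is a reason to show two restrictions and reconcile the text, not a reason to show none.

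Stronger readings are tempting. A reader might infer that scans taken soon after systemic steroids contaminate the primary result. The documents do not support that. The primary analysis population excludes asthma exacerbations and lower respiratory tract infections, so delays after exacerbation bear mainly on the evaluable set. Protocol 8.3.1 also separates the scan from treatment by at least 7 days. A reader might also infer that scans were taken after the dosing interval had lapsed. Under the regimen described in Protocol 4.3 a fourth dose would fall at week 16 (day 112), and no document shows a Visit 4 beyond that. The addendum says outside the window, not late; early visits are equally possible.

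**Conclusion.** The point holds as a gap in labelling and in sensitivity analysis. Following the plan as written gives an estimate described as Week 13 (± 5 days) that includes visits outside those days, with no bound and no means of seeing their influence.

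It is not shown that the estimate is biased, in either direction. The 0.75 to 1.25 range rests entirely on assumed values of f and r, and the precision figures rest on an assumed out-of-window share of the planned 29. The addendum refers to visit dates; taking this to include the week-13 CT scans is reasonable because CT is a Visit 4 procedure, but it is an inference. Nor do the documents show that effect estimates had been seen when the window was dropped, only that visit dates had.

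The change is worth making because it uses data already collected. It does not call the main analysis into question.

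**What to change.** Keep all Visit 4 data in the main analysis, and then:

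- Relabel the endpoint in SAP Tables 3 and 4 as change at Visit 4 (target week 13), and state that SAP 2.3.3 no longer applies to Visit 4.
- Report the distribution of actual Visit 4 study day, with the numbers early and late.
- Add two sensitivity analyses of the primary endpoint in both the primary and evaluable sets: one restricted to days 86–96, one to days 81–101 (the addendum's own boundary for an important deviation). Judge them by the estimate and interval rather than by the p-value.
- Reconcile the timing statements (± 5 days, ± 1 week, 4 to 6 weeks after Visit 3), including the completion wording that SAP 3.1.2.1 uses to describe the analysis sets, and give timing deviations a category in SAP 2.3.5.

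The cost is one summary of visit day, two short tables per population and some edits to text. The restricted sets will be smaller and less precise, so they should be described in advance as checks.

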1.3 Mucus Plug Subgroup

In section 3.1.2 of the SAP, sub-populations are outlined. The first of which is mucus plugging status. It is stated that a subgroup analysis will be conducted on those participants with (mucus plug score different from 0) and without (mucus plug score equal to zero) mucus plugs. In the final analysis this is to be updated to participants with greater than or equal to 4 mucus plugs and participants with strictly less than 4 mucus plugs.

1.4 FRI Parameters

Two secondary FRI parameters that are outlined in the protocol will be replaced by new ones in the final analysis. The two that are set to be replaced are listed below:

Developed from TP-BPM-WW-032; related to SOP-BPM-WW-001 D3250R00107

Statistical Analysis Plan Addendum

Parameter from Protocol	Description	Parameter from data transfer	Anticipated Data Selection Specifications
Trimmed distal specific siVaw at TLC (secondary)	Specific airway volume		
Trimmed distal specific siVaw at FRC (secondary)	Specific airway volume		

Table 2 Functional Respiratory Imaging Parameters (old)

They will be replaced by the following:

Tabla ²	3 Functio	nal Dasnir	otory Ime	aging Dara	motors (now)
I abic .	5 Functio	паі ксэрп	atory mil	aging 1 al a	meters (new)

Parameter from Protocol	Description	Parameter from data transfer	Anticipated Data Selection Specifications
Untrimmed distal iVaw at TLC (secondary)	Airway volume	-CCI	
Untrimmed distal iVaw at FRC (secondary)	Airway volume		

The rationale for this change is that there have been more and more insights in the mode of action of biologics in severe asthma. These compounds have greater effects on airway recruitment that can be related to reduced mucus plugging and decreased airway inflammation. In the past, FRI has been used in multiple studies evaluating the effects of inhaled medication in asthma, which

were used as a base when developing this protocol initially several years ago. Those compounds led to greater reductions in airway constriction, which would mostly be relevant when looking at trimmed airways, but more evidence became available that a reduction in bronchoconstriction is not the main driver for biologics. By focusing on the absolute airway volumes from untrimmed airway models there is greater understanding of the effects related to the airways opening up and bringing them within scan resolution after treatment.

1.5 Post-hoc Analysis

A post-hoc descriptive analysis may be conducted on airway wall thickness (the average thickness in mm calculated using an integral-based method. This endpoint is derived from distal airways, i.e., airways distal from the 3rd bifurcation) and Pi10 (the average square root of the cross-sectional wall area of a hypothetical airway of 10-mm lumen perimeter. This endpoint is also derived from distal airways).

Currently, airway wall volume (siVaww) is added in the SAP as an estimate for wall thickness. Quantitative measurements of airway wall volume and morphology have a robust history in the study of obstructive lung diseases, due to their demonstrated ability to detect subtly, spatially limited changes in airway patency related to inflammation, bronchoconstriction/dilation, and the presence of excess mucus. A shortcoming of this method is that it is influenced by airway diameter, i.e., if an airway is dilated its apparent wall volume will spuriously increase. Therefore, alternative endpoints have been developed that reflect the airway wall using different approaches: airway wall thickness (in mm) and Pi10.

Previous studies have shown that anti- IL-5 therapy may impact the extracellular matrix compound in the reticular basement membrane and the airway smooth muscle mass in the airway wall. Quantitative CT-derived measurements are therefore an important non-invasive tool to detect changes in airway wall thickness that may reflect a reduction in airway remodelling.

2 CHANGES TO THE STATISTICAL ANALYSIS PLAN

2.1 Baseline Definition

In Section 2.3.1 of the SAP, the baseline definition is outlined. It has been agreed, cross-functionally, that this definition should be updated in order to include those whose measurement was taken after study intervention of the same day. Hence, the updated baseline definition is:

• Baseline measurement is defined as the last measurement on or before the start day of study intervention administration.

2.2 Time Since Asthma Diagnosis

Section 3.1.6 of the statistical analysis plan provides an equation for the time since asthma diagnosis in years. This will be presented in months in the final TLF shells document so an updated equation for time since asthma diagnosis is.

Time since asthma diagnosis is calculated as follows:

(Date of Screening Visit 1 – Date of asthma diagnosis)/30.4375

2.3 Partial Dates for OCS Dependency

Section 3.2.1.8 of the statistical analysis plan (SAP) stated that the subgroup for the primary analysis is OCS dependency status. The definition of which is provided in Section 5.1 of the CSP, inclusion criteria number 4. The definition relies on being able to calculate how long each subject is OCS dependent but there are currently no rules for dealing with partial dates. Hence the following imputation rules for partial/missing dates will be applied to determine OCS dependency status:

2.3.1 Day is missing

For missing day there are two cases: Condition 1; both days are missing from the start and end date, Condition 2; day is missing from just one of the dates. In order to determine if the two dates are greater than or equal to 3 months apart, both the first day of the month and the last day of the month will be imputed. Then the OCS dependency time will be calculated for each condition:

- Condition 1:
 - Start date is imputed with the first day, end date is imputed with the last day
 - Start date is imputed with the last day, end date is imputed with the first day
- Condition 2:
 - Start day is imputed with the first day
 - Start day is imputed with the last day
 - End date is imputed with the first day
 - End date is imputed with the last day

If one of the above bullet points in each condition lead to the OCS duration being less than 3 months then OCS dependency cannot be determined. If all of the above bullet points for each condition lead to the calculation of duration greater than or equal to 3 months then it can be determined that OCS dependency was greater than or equal to 3 months.

2.3.2 Month is Missing

If the month is missing, then the duration of OCS dependency cannot be determined.

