5.1 Inclusion Criteria

Participants are eligible to be included in the study only if all the following criteria apply at Visit 0 (V0; screening visit):

Age

1 Participants must be 18 to 70 years of age inclusive.

Type of Participant and Disease Characteristics

- Participants who are diagnosed with asthma according to the American Thoracic Society (ATS)/European Respiratory Society (ERS) clinical guidelines (2014) (Chung et al., 2014), with documented reversibility post-bronchodilator (after 2 to 4 puffs of albuterol [in the US] or salbutamol [in other countries] see Section 8.1.2), either historical (medical records) or at Visit 0 (V0).
 - Reversibility is defined as an increment of ≥ 12% and ≥ 200 mL in FEV₁ and/or FVC compared with baseline during a single testing session in accordance with the 2005 ERS/ATS guidelines (Pellegrino et al., 2005).
- 3 Participants who have documented treatment with ICS and LABA for \geq 3 months prior to Visit 0 (V0), with or without oral corticosteroids and additional asthma controllers.
 - ICS and LABA can be components of a fixed dose combination product or given as separate inhalers.

- ICS dose must be > 500 μ g/day fluticasone propionate dry powder formulation or equivalent daily.
- For ICS/LABA combination preparations, the highest approved maintenance dose in the local country will meet this ICS criterion.
- Participants who have documented peripheral blood eosinophil count ≥ 300 cells/µL at Visit 0 (V0), or if OCS-dependent, a documented peripheral blood eosinophil count ≥ 150 cells/µL at Visit 0 (V0). For study sites in Belgium, all participants, irrespective of OCS-dependency must have a blood eosinophil count ≥ 300 cells/µL at Visit 0 (V0):
 - OCS-dependent asthma is defined as long-term OCS therapy (prednisone ≥ 5 mg/day for ≥ 3 continuous months directly preceding Visit 0 (V0) documented on medical records;
 - Are required to receive stable OCS dosage for \geq 4 weeks before Visit 0 (V0).
 - Alternate OCS dosing (e.g., every other day), other dosing frequencies, and OCS therapy other than prednisone/prednisolone are allowed provided the average daily dose is equivalent to ≥ 5 mg of prednisone.
 - Should remain on stable OCS dosing for the duration of the study.
- 5 Participants who have had a minimum of 2 exacerbations in the last 12 months prior to Visit 0.
 - Last exacerbation is required to be no less than 6 weeks before Visit 0 (V0)
 - Asthma exacerbation is defined by a worsening of asthma requiring:

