2.3.3 Year is missing

If only year is missing, then the year 2024 will be imputed solely for the duration calculation. The following intervals will determine OCS duration from the calculation OCS end date – OCS start date:

- 0<and<3 months: OCS dependency cannot be determined.
- >= 3 months: OCS duration is greater than or equal to 3 months.
- -12< and <-8: OCS dependency cannot be determined.
- -8<=and <=0: OCS duration was greater than or equal to 3 months.

These rules for partial dates can also be applied to determining the OCS dose relative to the screening visit.

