2.7 Linear Regression Model

In SAP sections 3.2.4 and 3.2.6, it states that more than just the intercept should be displayed in the final outputs however it is the intercept which is of interest and should be reported.

Linear regression models that have a population n < 10 will not be shown in the final outputs.

Throughout the linear regression sections of the SAP there is certain wording that requires more clarity. So, the following sections outline the number of model that should be used for each endpoint.

2.7.1 Secondary Endpoint 3 - Relationship Between Changes from Baseline in Airway Dynamics and Lung Functions Measurements at Week 13

The use of the word unadjusted in the SAP causes confusion over the number of models. Instead, the number of models is outlined explicitly. Three linear models will be fitted for each imaging parameter, where the endpoint will be change from baseline to week 13 in the imaging parameter:

- Model 1: Adjustment for baseline measurement of imaging parameter only
- Model 2: Adjustment for baseline measurement of imaging parameter and for change from baseline to week 13 in pre-BD FEV1
- Model 3: Adjustment for baseline measurement of imaging parameter and for change from baseline to week 13 in pre-BD FVC

CONFIDENTIAL

Developed from TP-BPM-WW-032; related to SOP-BPM-WW-001 D3250R00107

Statistical Analysis Plan Addendum

Table 4outlines the models that are expected for the analysis of tertiary endpoint 1.

Should there be no data for the assigned reference category then the most abundant category will be assigned as the reference.

Table 5 outlines all the of models expected for tertiary endpoint 2

Project Document Version No.: 3.0; Document Effective Date: 03 Sep 24 TP-GDO-WW-169-01 Effective Date: 22 Dec 21 Related to: SOP-GDO-WW-019 CONFIDENTIAL

Developed from TP-BPM-WW-032; related to SOP-BPM-WW-001 D3250R00107

Statistical Analysis Plan Addendum

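### SAP Addendum 2.3.2 declares OCS duration undeterminable whenever the month is missing, even when the recorded years prove at least 3 months

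*SAP*

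**What the plan says.** Inclusion criterion 4 (Protocol 5.1) supplies the definition: "OCS-dependent asthma is defined as long-term OCS therapy". It requires at least 5 mg/day of prednisone or equivalent for at least 3 continuous months directly before Visit 0, and a dosage stable for at least 4 weeks before Visit 0. SAP 3.2.1.8 uses this definition to form two subgroups, OCS-dependent and non-OCS-dependent. SAP 3.2.2.8, 3.2.3.7 and 3.2.4.7 carry the same subgroups to secondary endpoints 1, 2 and 3.

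Addendum 2.3 notes that the SAP had no rule for partial dates and states that "the following imputation rules for partial/missing dates will be applied to determine OCS dependency status". Three cases follow:

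- **Day missing (2.3.1):** "both the first day of the month and the last day of the month will be imputed". If every combination gives at least 3 months, the duration is accepted. If any falls short, it is undeterminable.
- **Month missing (2.3.2):** "If the month is missing, then the duration of OCS dependency cannot be determined". That sentence is the whole rule.
- **Year missing (2.3.3):** "If only year is missing, then the year 2024 will be imputed solely for the duration calculation". Intervals of the resulting difference are then mapped either to at least 3 months or to undeterminable.

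Neither the Addendum nor the SAP says what happens in the two-category subgroup to a participant whose status is undeterminable.

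**The concern.** Rule 2.3.1 asks whether the duration reaches 3 months under every date consistent with the record. Rule 2.3.2 stops asking that question. A date recorded as a year only is less precise than one that lacks just the day, but the threshold is 3 months and years of use can clear it by a wide margin. A programmer following 2.3.2 as written must still return no duration.

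What is at stake is the classification for one of the two planned subgroup factors. A participant could enter the trial as OCS-dependent, with the history documented at Visit 0 as Protocol 6.5 requires, and have no OCS duration when the subgroup is derived. Because the handling is unstated, two programmers could treat that participant differently. Leaving the participant out shrinks the OCS-dependent group. Counting the participant as non-dependent mixes a possibly dependent patient into the comparison group.

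**Working it through.** The plan gives no figure to reproduce. The check is whether a record with no month can still settle the 3-month question under the plan's own bounding logic.

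**Inputs**

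- Threshold: at least 3 months (Protocol 5.1, criterion 4).
- Method: earliest and latest possible date, accepted only if all cases pass (Addendum 2.3.1).
- Days per month: 30.4375, the Addendum's own conversion in 2.2.
- Reference date, for use ongoing at Visit 0: 15 June 2023. This is an assumption, because the documents give no participant dates.

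**The 2.3.1 rule as written (day missing, end date 15 June 2023)**

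- Start January 2023: 4.4 months (from 31 January) to 5.4 months (from 1 January). Both pass, so the duration is accepted.
- Start March 2023: 2.5 to 3.5 months. The bounds straddle 3, so it is undeterminable.

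**The same rule extended to a missing month**

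Minimum duration = (reference date − 31 December of start year) / 30.4375, with the latest start capped at the reference date. Maximum duration = (reference date − 1 January of start year) / 30.4375.

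For a 2018 start, 31 December 2018 to 15 June 2023 is 1,627 days, and 1,627 / 30.4375 = 53.5 months.

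| Recorded start year | Minimum (months) | Maximum (months) | Bounds show | 2.3.2 returns |
|---|---|---|---|---|
| 2015 | 89.5 | 101.4 | at least 3 | undeterminable |
| 2018 | 53.5 | 65.4 | at least 3 | undeterminable |
| 2020 | 29.4 | 41.4 | at least 3 | undeterminable |
| 2021 | 17.4 | 29.4 | at least 3 | undeterminable |
| 2022 | 5.5 | 17.4 | at least 3 | undeterminable |
| 2023 | 0.0 | 5.4 | straddles 3 | undeterminable |

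Only the last row is truly open.

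**Both dates year-only**

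Minimum = (1 January of end year − 31 December of start year) / 30.4375. This gives 48.0 months for 2018 to 2023, 24.0 for 2020 to 2023 and 12.0 for 2021 to 2023. For 2022 to 2023 it is about 0, so that case is open.

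**Sensitivity to the reference date**

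A start in the calendar year just before the reference date is open only when the reference date falls in roughly the first three months of its year:

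- 1 February 2023: 32 / 30.4375 = 1.1 months, open.
- 31 March 2023: 90 / 30.4375 = 2.96 months, just short.
- 2 April 2023: 92 / 30.4375 = 3.02 months, settled.

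Starts two or more calendar years back are settled for any reference date, with a minimum of about 12 months.

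**The case against.** The strongest reply is that the impact is small and may be nil. The documents give no count of records with a missing month. The rule touches subgroups only: the overall paired t-test does not use OCS status, and the tertiary endpoints do not use this subgroup (SAP 3.2.5.6, 3.2.6.6 and 3.2.7.6). Protocol 6.5 also requires the OCS history to be in the source record and eCRF at Visit 0, so the status is recoverable. All of this stands as a limit on size. It does not remove the inconsistency, because Addendum 2.3 says its own rules decide the status and 2.3.2 makes no reference to that record.

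Several stronger readings are tempting but not supported:

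- **Affected participants lose their dependent status.** The text says the duration is undeterminable. It does not say they become non-dependent or are dropped.
- **A long elapsed time proves dependence.** It settles duration only. The dose and stability parts of criterion 4 remain to be checked.
- **The rule selects against the longest users.** Year-only dates may be commoner for long-standing treatment, but nothing in the documents shows this.
- **The OCS-dependent subgroup will fall below the reporting limit.** Addendum 2.7 says "Linear regression models that have a population n < 10 will not be shown in the final outputs". No OCS subgroup size is given, and the limit covers linear regressions only. Those regressions use the baseline endpoints set (secondary endpoint 2) and the primary analysis population (secondary endpoint 3), so a calculation from the 34 evaluable participants would be misplaced.
- **2.3.2 is wrong because 2.3.3 can return a result with less information.** With only the year missing, the interval is known up to whole years, which is different information. The comparison that carries weight is with 2.3.1.
- **The 2024 imputation misplaces OCS use relative to screening.** Section 2.3.3 confines 2024 to the duration calculation, then adds: "These rules for partial dates can also be applied to determining the OCS dose relative to the screening visit". That sentence is permissive and ambiguous. It merits a clarification, not a finding.

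**Conclusion.** The point holds. Section 2.3.2 discards durations that the recorded years prove, and it is inconsistent with the bounding rule in the section before it. In the illustrations above, year-only starts from 2015 to 2022 all clear 3 months at a mid-2023 reference date, by margins from 2.5 months (5.5 − 3) to 86.5 months (89.5 − 3).

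The consequence is confined to the OCS-dependency subgroup analyses of the primary endpoint and secondary endpoints 1 to 3. The number of participants affected is unknown. The direction of any effect on the subgroup results cannot be stated either, because the plan does not say where undetermined participants go. The conclusion rests on the wording of the two rules; the calendar dates are illustrations and do not drive it. The change is worth making because it is cheap and the subgroup derivation is incomplete without it.

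**What to change.** 1. Replace 2.3.2 with the 2.3.1 bounds. Impute a missing month as 1 January and as 31 December of the recorded year, capped at the other date or, for ongoing use, at Visit 0. If every case reaches 3 months, the duration criterion is met. Still check the dose and stability parts of criterion 4.
2. Keep the undeterminable result only where the bounds straddle 3 months. In those cases use the criterion 4 OCS history recorded in the eCRF at Visit 0 (Protocol 6.5).
3. State how any participant still undetermined is handled in the two-category subgroup, and report the number.
4. As a side clarification, state in 2.3.3 that the imputed year 2024 is not used to position OCS use relative to the screening visit.

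The cost is a few sentences in the Addendum and a small change to the derivation program. No new data are needed.
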